6.7.4. Multiple Assessments

For detection of clinical abnormalities all available data including from unscheduled visits will be used and if summarized by timepoint, the most abnormal value will be considered. When summarizing low and high abnormality, both most abnormal low and high values will be displayed separately in 6 categories (missing, clinically significant low, not clinically significant low, normal, not clinically significant high, clinically significant high). If a subject had both low and high abnormalities, then only the worst value would be displayed in the appropriate category of the abnormality and shift tables, but all abnormalities will be identified in the listings.

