8.3. Routine Laboratory Data

The analyses of the safety laboratory will be performed using the Safety Population. Multiple assessments within a visit or time interval will be handled as described in [Section 6.7.4](#).

Mean Changes and % Changes from baseline to each post baseline timepoint in each laboratory assessment that is a continuous variable will be summarized along with other descriptive statistics for continuous variables.

Additionally, chemistry and hematology parameters will be categorized as low, normal or high according to laboratory range specifications. In addition, Investigator assessment of whether the abnormality was clinically significant will be recorded.

The number and percentage of subjects will be presented at each assessment time point for the safety population using the following categories:

- missing data
- clinically significant low abnormality
- non-clinically significant low abnormality
- normal values
- non-clinically significant high abnormalities
- high clinically significant abnormalities

In addition shift Tables will summarize clinically significant abnormalities between baseline and post baseline value using the above categories and the worst values post baseline. Note, this tabulation is not by visit.

Urinalysis tests that are recorded as continuous parameters like pH and specific gravity will be analyzed as above. All other urinalysis parameters will just be included in the listings.

Coagulation parameters will be analyzed as above.

Laboratory values outside the normal range will be displayed in a separate listing with clinically significant values flagged. Determination of clinical significance will be made by the Investigator and recorded in the eCRF.

Laboratory parameter units will be standardized to conform to the Table below:

Laboratory parameters for safety investigations will be analyzed in the standardized units given below:

Blood Biochemistry:

• Alkaline phosphatase	U/L
• Alanine aminotransferase (ALT)	U/L
• Aspartate aminotransferase (AST)	U/L

BrainStorm Cell Therapeutics Ltd.
Statistical Analysis Plan - Protocol BCT-101-US

April 12, 2019

• Bicarbonate	mmol/L
• Blood urea nitrogen (BUN)	mg/dL
• Calcium	mmol/L
• Chloride	mmol/L
• Creatinine	µmol/L
• Glucose	mmol/L
• High-Density Lipoprotein (HDL) Cholesterol	mmol/L
• Low-Density Lipoprotein (LDL) Cholesterol	mmol/L
• Potassium	mmol/L
• Sodium	mmol/L
• Total Bilirubin	µmol/L
• Total Cholesterol	mmol/L
• Uric Acid	mg/dL

Hematology:

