3. STUDY ASSESSMENTS

3.1 Handling of Safety or Efficacy data

- If subject discontinues during study (Early Termination) at any visit, then any collected (safety and efficacy) data under EOS/Visit 7 (Week28) will be re-mapped to nearest scheduled visit as per Schedule of Assessment (SoA). If this visit has data already recorded then data will be remapped to the next visit following this nearest visit. This is applicable for all safety and efficacy analysis.
- No imputations will be performed on missing efficacy or safety data except for visits as defined in the SAP. Sensitivity analyses may be performed with imputations after the database is locked.
- The baseline visit will be defined as the most recent assessment prior to receiving the first treatment at Visit 3 considering scheduled and unscheduled visits.
- Handling of unscheduled visits for Laboratory and Vital Summary by timepoints- In change from baseline (CFB), % CFB and Abnormality analysis by visit tables, data collected at unscheduled visits will not be summarized since there are only 2 subjects with unscheduled visit data at pre-treatment visits and no unscheduled post-treatment.

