4.2 Laboratory data

SAP section 8.3 incorrectly stated SI Unit for Uric Acid as mg/dL. The correct SI is $\mu\text{mol}/\text{L}$ and will be used.

Lab abnormalities:

For analysis of abnormalities across multiple visits such as shift Tables, the worst value will be considered. Lab data will be tabulated using categories below:

1. missing data
2. clinically significant low abnormality
3. non-clinically significant low abnormality
4. normal values
5. non-clinically significant high abnormalities
6. high clinically significant abnormalities

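### The laboratory shift table keeps one undefined worst value, so a participant low at one visit and high at another loses one direction from it

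*SAP*

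**What the plan says.** SAP 6.7.4 gives two consecutive rules for repeated assessments. The first is that "both most abnormal low and high values will be displayed separately in 6 categories". The second is: "If a subject had both low and high abnormalities, then only the worst value would be displayed in the appropriate category". That second rule covers both kinds of table and leaves the full record to the listings: "of the abnormality and shift tables, but all abnormalities will be identified in the listings". The six categories are missing, two grades of low, normal and two grades of high, graded by clinical significance.

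SAP 8.3 applies this to laboratory data: "Multiple assessments within a visit or time interval will be handled as described in" section 6.7.4. It then plans two kinds of table:

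- A by-visit abnormality table: "The number and percentage of subjects will be presented at each assessment time point for the safety population using the following categories".
- A shift table from baseline, "using the above categories and the worst values post baseline. Note, this tabulation is not by visit".

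Section 8.3 also plans a listing of every out-of-range value, with clinically significant values flagged.

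Appendix I section 4.2 returns to the rule: "For analysis of abnormalities across multiple visits such as shift Tables, the worst value will be considered". It repeats the six categories. It does not rank them, and it does not withdraw the promise of separate display.

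**The concern.** For a participant abnormal in both directions on one analyte, the two sentences of 6.7.4 give different tables. That participant is also the only one for whom showing both extremes separately makes a difference.

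The second sentence, which the later text follows, cannot always be carried out. Low and high lie on opposite sides of normal. When the flags differ, it is natural to treat the clinically significant value as worse, although the plan does not say so. When the flags are the same, nothing identifies the worse value and the choice falls to the programmer.

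Safety is the primary objective, and SAP 3.2.1 names changes in hematology and blood chemistry in the primary endpoint. The shift table is the planned abnormality summary that pools visits within a participant. A low at one dosing visit followed by a high at the next is a pattern such a table should be able to show.

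**Working it through.** The plan gives no figure to reproduce. The check has three parts.

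**1. One assumed participant.** Potassium is clinically significantly low at Visit 4 and clinically significantly high at Visit 5.

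| Output | Entries | Which |
|---|---|---|
| Shift table, both extremes separately | 2 | low and high |
| Shift table, single worst value | 1 | not determined by the plan |
| By-visit abnormality table | 2 | low at Visit 4, high at Visit 5 |
| Listings | 2 | both |

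If all 20 planned participants are in the Safety Population, one omitted entry lowers its shift-table category by 1/20 = 5.0 percentage points.

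**2. Where it can happen.** These inputs come from the schedules (Protocol Table 1, SAP Table 2) and the analyte lists in SAP 8.3.

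- Hematology, coagulation and chemistry are scheduled at Visits 3, 4, 5 and 7. Visit 3 bloods are drawn before the first treatment, so they are baseline. That leaves 3 post-baseline values.
- Analytes repeated at all three visits: 15 hematology + 6 chemistry (sodium, potassium, chloride, glucose, BUN, creatinine) + 3 coagulation = 24.
- Chemistry analytes scheduled only at Visits 1 and 7, such as AST and ALT, have one post-baseline value. It cannot be both low and high.
- Participant-analyte pairs at risk: 20 × 24 = 480.
- In the by-visit table, a loss needs both directions within one timepoint. Each visit has one scheduled draw. Appendix I section 3.1 says of these tables that "data collected at unscheduled visits will not be summarized since there are only 2 subjects with unscheduled visit data at pre-treatment visits", and it reports no unscheduled data after treatment. No by-visit loss is therefore expected.

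**3. Illustrative size.** Let p be the chance of a low, and also of a high, at any one visit, with visits independent. The documents give no value for p, so I assume 2%, 5% and 8%.

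P(at least one low and at least one high in 3 visits) = 1 − 2(1 − p)³ + (1 − 2p)³

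- p = 0.02: 1 − 2(0.941192) + 0.884736 = 0.0024; × 480 = 1.1
- p = 0.05: 1 − 2(0.857375) + 0.729000 = 0.0143; × 480 = 6.8
- p = 0.08: 1 − 2(0.778688) + 0.592704 = 0.0353; × 480 = 17.0

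Spread over 24 analytes, the highest figure is 17.0/24 = 0.71 of a participant per analyte. The total does not depend on independence between analytes, but it does depend on independence between visits.

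**The case against.** The best defense reads the two sentences as a rule and its exception: low and high are separate categories, and a participant with both is counted once, at the worst. Appendix I, the later text, keeps the single value. A shift table that places each participant once is a legitimate design, no test or decision depends on it, and a one-line tie-break would make it workable. This narrows the conflict but does not remove the problem. The word *both* fits the exception reading poorly, and even under that reading *worst* is undefined when the flags match.

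The defense is also right that most of the information survives elsewhere. A reader might infer from 6.7.4 that one of the two abnormalities leaves all the laboratory tables and remains only in listings. The documents do not support that. SAP 8.3 tabulates the categories at each timepoint, so opposite values at different visits each appear at their own visit. Change from baseline is also summarized by timepoint, with minimum and maximum. In addition, Protocol 7.1.7 sends any abnormality the investigator deems clinically significant to the adverse event form, so those arising after first treatment reach the adverse event tables.

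A reader might also count four post-baseline laboratory visits, because Protocol 4.4 speaks of monitoring at Visits 1–7. At p = 0.05 that would give 1 − 2(0.95)⁴ + (0.90)⁴ = 0.0271, or 13.0 pairs, about double. But 4.4 defers to the schedule, which has no safety laboratory tests at Visit 6, and Protocol 4.8.2 lists only biomarker blood there.

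Finally, the illustration is soft. Repeat values in one person tend to stay on the same side of the range, so low-then-high is probably rarer than independence implies. Ten of the 24 analytes are five cell types reported both as a percentage and as an absolute count, so the entries are not 24 separate pieces of information.

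**Conclusion.** The point holds for the pooled shift table only. SAP 6.7.4 gives two display rules that differ for a participant abnormal in both directions. The single-worst rule that SAP 8.3 and Appendix I 4.2 carry forward drops one direction, and it does not determine which when the clinical-significance flags match.

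The exposure is limited to the 24 analytes with values at Visits 4, 5 and 7. The illustrative loss is about 1, 7 or 17 entries among 480 participant-analyte pairs. This rests on assumed rates of 2%, 5% and 8% per direction per visit, independence between visits, and all 20 participants treated and measured. The counts are more likely too high than too low.

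This is a minor reporting defect in a descriptive, single-arm study. It is worth correcting because safety is the primary objective and the correction is cheap.

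**What to change.** In SAP 6.7.4, SAP 8.3 and Appendix I 4.2, replace the single-worst rule for shift tables with two shifts per analyte: baseline category to lowest post-baseline category, and baseline category to highest post-baseline category. Count each participant once in each, so that percentages within each table still add to 100%. No ranking of low against high is then needed, and the separate display promised in 6.7.4 is delivered. The by-visit abnormality tables and the listings need no change.

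If the sponsor prefers a single shift table, the minimum repair is to state one rule, define *worst* across directions, and footnote any participant abnormal in both. That makes the rule workable but still leaves one direction out of the body of the table.

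The cost of the two-shift version is a short text change and one more shift table per laboratory panel. It uses data already collected.

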6.8. Handling of Missing Data

Missing values with the exception of dates will not be imputed.

6.8.1. Missing Start and Stop Dates for Adverse Events and Concomitant Medications

The following imputation rule will be used in this study:

For onset or start dates as well as end or stop dates for AEs or Medications, a conservative approach will be used, where if an event can be considered as being on treatment it will be assumed to be so.

For onset or start dates for AEs or Medications, the following rules will be used to impute partial dates:

- a) If month and year are known, but the day is unknown, the day will be assumed to be the 1st, unless the treatment was started that month of the same year in which case the day will be set to the day of start of treatment.
- b) If only the year is known but both day and month are missing, the day and month will be assumed to be 1st January, unless the treatment started that year, in which case the day and month will be imputed to be the treatment start day and month.

For end or stop dates the following will be used to impute partial dates:

- a) If month and year are known, but the day is unknown, the day will be assumed to be the last day of the month, unless the date of last treatment is in the same month and year, in which case the day of last treatment will be used to impute the end or stop day.
- b) If only the year is known but both day and month are missing, the day and month will be assumed to be 31st December, unless the date of last treatment is in the same year, in which case the day and month of last treatment will be used to impute the end or stop day and month.

In addition:

If an AE start date is completely missing or it is unclear whether the event occurred prior to or in the treatment period, the AE will be assumed to be treatment emergent (after initiation of first treatment).

If a medication end date is completely missing or it is unclear whether the medication was taken prior to or in the treatment period, the medication will be assumed to be taken during the treatment period as a “concomitant medication”.

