8. SAFETY AND TOLERABILITY

All safety analyses will be based upon the Safety Population.

All AEs will be coded to SOC and PT using the MedDRA, version 21.1.

A Treatment-emergent adverse event (TEAE), referred to subsequently as just TEAE or AE is an AE that occurs for the first time after initiation of first treatment or if it had occurred prior to initiation first treatment, it worsens in severity after initiation of first treatment.

AE's that occur prior to initiation of first treatment will only be in the listings and not included in any summary Tables.

AE's related to the Bone Marrow Aspiration will be included in a separate listing.

When evaluating changes in continuous safety parameters (such as laboratory measurements, vital signs, ECGs, etc.) , Baseline will be defined as the last measurement prior to first transplantation (i.e., prior to initiation of treatment).

Additional details for analysis of safety data are detailed below.

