3.4 Prior and Concomitant Medication

PRIOR AND CONCOMITANT MEDICATIONS

The definition of a prior medication is defined as any medication taken prior to the date of first treatment and either stopped prior to the first treatment or continued after it.

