4. SAFETY ANALYSES

4.1 Adverse Event

- Adverse Event will be coded using the MedDRA, version 23.1 instead of 21.1 as mentioned in SAP section 8.
- Summary for MS relapse will not be done separately in table/listing due to lack of data.
- As mentioned in section 8 of SAP, Treatment-emergent adverse event (TEAE) is an AE that occurs for the first time after initiation of first treatment or if it had occurred prior to initiation first treatment, it worsens in severity after initiation of first treatment. In current TEAE analysis all AEs with onset date after initiation of first treatment are considered as TEAEs irrespective of severity.

- The AE eCRF page assesses discontinuation from treatment (and not from study) while the End of Study (EoS) eCRF page assesses if a subject was discontinued from the study, hence there may be differences between what is recorded on these eCRF pages.. The disposition Table will display the number of subjects discontinued from study as recorded on the end of study page. No AE Tables will be generated for AEs leading to study discontinuation as this data was not collected in the AE eCRF. A listing will provide AE's from the AE datasets for subjects who discontinued the study based on an AE as recorded in the end of study page
- Certain tables will not be generated since there are too few subjects (example procedure related adverse events etc.). But subjects with these AE criteria's will be summarized in listings.

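### SAP 6.8.1 imputes partial dates without checking the event's other known date, so an AE that ended before dosing can be tabulated as treatment-emergent and an event that began after the last dose can be given a stop before its start

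*SAP*

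**What the plan says.** SAP 6.8.1 opens with a general principle for AE and medication dates: "if an event can be considered as being on treatment it will be assumed to be so". Itemised rules follow.

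- **Start, day unknown:** first of the month, unless treatment began in that month and year, "in which case the day will be set to the day of start of treatment".
- **Start, day and month unknown:** 1 January, unless treatment began in that year, "in which case the day and month will be imputed to be the treatment start day and month".
- **Stop, day unknown:** last day of the month, unless the last treatment falls in that month and year, "in which case the day of last treatment will be used to impute the end or stop day".
- **Stop, day and month unknown:** 31 December, unless the last treatment falls in that year, "in which case the day and month of last treatment will be used to impute the end or stop day and month".

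A closing clause makes an AE treatment-emergent when its start is wholly missing or its timing relative to treatment is unclear. SAP Appendix I, section 3.5, adds a default of January for a missing month and nothing else. The protocol has no partial-date rule.

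Two further statements decide what follows from an imputed onset. SAP section 8 says "AE's that occur prior to initiation of first treatment will only be in the listings". Appendix I, section 4.1, says that in the analysis as run "all AEs with onset date after initiation of first treatment are considered as TEAEs irrespective of severity".

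**The concern.** Each rule uses the treatment date and the known part of the date being completed. None uses the other date of the same event, even when that date is fully recorded.

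For starts, this can override information that settles the question. A recorded stop before the first dose shows that the event was over, yet the rule puts its onset on the dosing date. TEAE status is decided by onset, and pre-treatment AEs are kept out of the summary tables, so the error moves an event from a listing into a table. AEs are one component of the primary safety endpoint (Protocol 9.1.1, SAP 3.2.1). Pre-dose AEs will be on file: collection starts at consent (Protocol 7), the first dose comes 6 to 10 weeks after screening, and the bone marrow aspiration falls in between (Protocol 2.1).

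For stops, the last-treatment exception pulls the date back to the last dose, although participants are followed for 12 more weeks. An event that begins in that follow-up can be shown as ending before it began.

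**Working it through.** There is no stated figure to reproduce. The check applies the four rules literally to worked dates, then counts how often they misfire.

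**Inputs.** Rules from SAP 6.8.1. Doses at weeks 0, 8 and 16, pre-dose period 6 to 10 weeks (42 to 70 days), follow-up 12 weeks (84 days), all from Protocol 2.1. Assumed calendar for the examples: first dose 20 Sep 2019; last dose 112 days later, 10 Jan 2020.

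| Case | Recorded | Imputed by 6.8.1 | Result |
|---|---|---|---|
| A | start Sep 2019, stop 8 Sep 2019 | start 20 Sep 2019 | onset 12 days after the event ended, on the dosing date |
| A2 | start 2019, stop 20 Aug 2019 | start 20 Sep 2019 | onset 31 days after the event ended |
| B | start 15 Jan 2020, stop Jan 2020 | stop 10 Jan 2020 | stop 5 days before start |
| B2 | start 19 Feb 2020, stop 2020 | stop 10 Jan 2020 | stop 40 days before start |

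**Consequence of A and A2.** An imputed onset on the dosing date, with TEAE status set by onset alone, puts the event in the TEAE tables. This assumes that an onset on the dosing date counts as after initiation, which is the evident purpose of the rule. One subject in 20 is 1/20 = 5 percentage points.

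**Consequence of B and B2.** TEAE status does not use the stop date. SAP 8.1 and 8.2 plan no summary of AE duration. A medication stop moved to the last dose is still on or after the first dose, so the drug stays concomitant. Only the displayed dates are wrong.

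**How often, given a partial date.** Assumptions: one-day events on each day of the window, the other date fully known, and first-dose dates on each of the 366 days of 2020.

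- *Start, day missing.* Misfires when the event and the first dose share a calendar month. Summing the earlier days of the month over all dose dates: 7 × 465 + 4 × 435 + 406 = 5,401. Share: 5,401/(366 × 42) = 35%; 5,401/(366 × 70) = 21%.
- *Start, day and month missing.* Misfires when they share a year. 42 days: (903 + 323 × 42)/15,372 = 14,469/15,372 = 94%. 70 days: (2,485 + 295 × 70)/25,620 = 23,135/25,620 = 90%.
- *Stop, day missing.* 5,381/(366 × 84) = 5,381/30,744 = 18%.
- *Stop, day and month missing.* 27,174/30,744 = 88%.

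These are conditional shares. They do not estimate how many records are affected.

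**With each imputed date bounded by the known one.** Case A: the earlier of 20 Sep and 8 Sep is 8 Sep 2019, before dosing, so not treatment-emergent. Case B: the later of 10 Jan and 15 Jan is 15 Jan 2020, so no inversion.

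**The case against.** The strongest reply is that the opening principle already governs. An event known to have ended before dosing cannot be on treatment, its timing is not unclear, and SAP section 8 sends pre-dose AEs to listings. A careful programmer might therefore never apply the start rule to it. This stands in part: the miscount is a result of the literal rule, not a certainty. But the itemised rule is explicit and carries no such exception, so two programmers could code it differently. The principle is a reason to write the bound down.

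Mitigations also count. SAP 6.1 has listings show both the partial and the imputed date, so the error is visible. Aspiration-related AEs get their own listing (SAP section 8), though nothing there expressly removes them from the TEAE tables. Protocol 12.2.1 provides consistency checks, which may reduce partial dates; the plan does not say that they are run on imputed ones. Each subject counts once per row (SAP 8.2), so the 5-point shift applies only where the subject is not already counted.

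A reader might infer four stronger things that the documents do not support:

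- *That TEAE counts are the primary endpoint.* SAP 3.2.1 and Protocol 9.1.1 also include vital signs, examinations, laboratory tests, MRI and concomitant medications.
- *That a drug stopped before dosing loses its prior status.* Appendix I, section 3.4, defines prior as "any medication taken prior to the date of first treatment and either stopped prior to the first treatment or continued after it". A known pre-dose stop already satisfies this, whatever start is imputed.
- *That the stop rule breaks the section's conservatism.* The section uses that word for attribution to treatment, not for longest duration.
- *That the stop rule distorts a planned duration analysis.* None is planned.

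**Conclusion.** The point holds as a gap in the imputation rules. Taken literally, the start rule can place the onset of an AE known to be over before dosing on the dosing date, and so in the TEAE tables. The effect on one incidence row is at most 5 percentage points per misclassified subject with 20 treated. It requires a partial start, a known pre-dose stop, a programmer who follows the itemised rule, and an onset on the dosing date being counted as after initiation. The stop rule can produce a stop before a known start; that is a matter of date consistency in the listings only. The number of partial dates is not given, so nothing here shows that the reported safety results are materially distorted. The correction is worth making because a stated rule gives a wrong answer when the recorded data already hold the right one.

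**What to change.** Add to SAP 6.8.1:

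> An imputed start date will not be later than a known stop date, and an AE or medication with a known stop before first treatment is classed as pre-treatment (AE) or prior (medication); an imputed stop date will not be earlier than the start date.

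In code this is a minimum on the start, a maximum on the stop and one classification check. Events whose timing is truly ambiguous remain treatment-emergent, as the section intends. If the datasets are already programmed, list records with an imputed start after a known stop, or an imputed stop before a known start; an empty list shows that no record has inverted dates.

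Do not also cap imputed stop dates at the end of study. Protocol 7.1.5 follows SAEs to resolution or stabilisation, which may come later, and Protocol 8.2 allows AEs after discontinuation to be recorded within 12 weeks of the last transplant. A cap could overwrite a known later stop month or put the stop before the start again.
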